6.1.6 Cardiac Autonomic Function Measures

To guide exploration of changes in autonomic nervous system function as a potential mediator of intervention effects in women with incontinence, participants will undergo the following measures at baseline and 12 weeks. During the COVID-19 pandemic, participants may decline to undergo these measurements that require them to come into close proximity (less than 6 foot distance) with study personnel.

- A. High frequency heart rate variability (a.k.a. respiratory sinus arrhythmia, or RSA) refers to the degree to which heart rate accelerates and decelerates during the respiratory cycle, and has been shown to be a reliable marker of cardiac parasympathetic activity.⁷¹⁻⁷³ Evaluation of rest-to-stress changes in RSA allows for assessment of abnormalities in adaptive vagal regulation, previously shown to be associated with bladder instability and urine leakage in response to stressful events.²⁰⁻²² Procedures for assessing RSA, monitoring data quality, and interpreting findings have been designed by co-investigator [name], who has authored one of the main textbooks on autonomic assessment,⁷⁴ published four methodological articles and chapters on this topic,⁷⁵⁻⁷⁸ and collaborated with the research team on other NIH-funded studies.⁷⁹ Heart rate variability measurements will be obtained according to standard protocols from the North American Society of Pacing & Electrophysiology,⁸⁰ in which two ECG electrodes will be attached to each participant's right and left wrists using pre-gelled sensors while in the seated position. Following an initial 10-minute "resting" recording, a 10-minute "stress" recording will be obtained while the participant completes two stress tasks, including a visual attention and tracking task⁸¹ shown to reliably induce vagal

withdrawal in subjects across the lifespan.^{75,76} Analyses using Mindware software will examine both resting and rest-to-stress change in RSA.

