6.1.7 Pelvic Floor Muscle Strength

To guide exploration of changes in pelvic floor muscle strength as a potential mediator of intervention effects in women with incontinence, participants will be invited to undergo the following optional assessment of pelvic floor muscle strength at baseline and 12 weeks. For this assessment, a clinically-trained assessor (doctor, nurse, or pelvic floor physical therapist) will perform a digital pelvic exam and ask the participant to squeeze her pelvic floor muscles during exam. The assessor will then rate pelvic muscle strength using the Brink scale, which includes 4-point scales in 3 categories—contraction pressure, displacement of the examiner's fingers, and duration of squeeze—to create an overall score of 0 to 12.⁸⁴⁻⁹⁰ Since this is an optional assessment, participants who have a relative contraindication to pelvic exam or anticipate pain with pelvic exam can decline to undergo this measurement. During the COVID-19 pandemic, participants may also decline to undergo these measurements that require them to come into close proximity (less than 6 foot distance) with study personnel. For assessments performed after randomization, the assessor will be blinded to intervention assignment.

At the Stanford clinical site, participants will also be invited to undergo perineometer assessment of pelvic floor muscle strength by a board-certified urogynecologist at the same timepoints (baseline and 12 weeks). Participants will be asked to contract their pelvic floor muscles, and contraction strength will be measured with a Laborie Urostym digital perineometer. This device is currently used clinically and approved for pelvic floor physical therapy and biofeedback. Measurements obtained by perineometer have previously been shown to have good inter-rater and test-retest reliability. Measurements will include minimum, maximum, and average strength of each pelvic floor muscle contraction measured. Duration of contraction will also be recorded. A total of three contractions will be measured by digital perineometry. Measurements

will be recorded in cm H₂O or mm Hg. Each patient will be assigned a vaginal sensor that will be processed according to manufacturer's recommendation and used for the baseline and follow-up exams. Since this is an optional assessment, participants who have a relative contraindication to pelvic exam or anticipate pain with pelvic exam can decline to undergo this measurement.

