9.6 Data Analyses

9.6.1 Analyses to address main objectives

Objective 1: To determine the efficacy of a group-based yoga intervention in reducing the frequency of urinary incontinence in ambulatory midlife and older women.

Hypothesis 1A: Ambulatory incontinent women randomized to the yoga intervention will demonstrate at least a 20% greater decrease in total incontinence frequency (measured by validated voiding diaries) over 12 weeks, compared to women randomized to the control intervention.

Hypothesis 1B: If improvements in total incontinence frequency are observed at 12 weeks, these improvements will be sustained 12 and 24 weeks after the end of the intervention programs.

Planned analyses: Intervention effects on the primary outcome of total incontinence frequency will be estimated using a linear mixed model (LMM) for changes since baseline in the overall frequency of any incontinence episodes at 6 and 12 weeks, adjusting for baseline incontinence frequency. Analyses will be by intention to treat, according to intervention group assignment, and without regard to adherence to intervention classes or practice. The LMM will account for clustering using nested random effects for group intervention class series and individual participant. In addition to fixed effects for study location and type of incontinence, the LMM will include terms for intervention, time, and the time-by-intervention interaction, thus allowing for secular trends in controls, as well as different intervention effects at 6 and 12 weeks. The intervention effect will be summarized by an orthogonal contrast capturing any linear trend across 6 and 12 weeks; this makes use of information for participants with 6 but not 12 week outcomes. If the yoga intervention appears effective over 12 weeks, we will also assess maintenance of effects over time, by comparing changes since baseline at 12 weeks with those at 24 and 36 weeks, using an additional LMM. Intervention effects will again be summarized by an orthogonal contrast for linear trend across the three time points.

Objective 2: To determine the efficacy of a group-based yoga intervention in reducing the frequency of type- and context-specific urinary incontinence in ambulatory middle-aged and older women.

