Planned analyses: Additional intermediary outcomes include pelvic floor muscle strength (measured by Brink scale), peripheral autonomic function (reflected by respiratory sinus arrhythmia [RSA] and cardiac pre-ejection period [PEP] parameters), and lower extremity physical function (assessed using the Short Physical Performance Battery [SBBP] and 2-minute step test). Intervention effects will first be estimated using LMMs, using the same modeling strategy used for objectives 1-3. Next, to assess for mediation of changes in incontinence frequency by changes in these factors, we will assess correlation between changes in these

parameters and change in incontinence frequency between baseline and 12 weeks. We will then examine attenuation of intervention effects estimates from the primary intention-to-treat analyses after adjustment for these potential mediators. Mediators will initially be analyzed as continuous variables (i.e., continuous change in RSA and PEP), but categorization will be considered in the event of skewed variable distributions. If evidence of mediation is observed, we will estimate 95% bias-corrected percentile confidence intervals for the proportion of intervention effect explained, using resampling by participant to fully account for the correlation between intervention effect estimates before and after adjustment for change in the mediators

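### The Objective 4 mediation step adjusts for change in the mediator but not its baseline value, so the share of the yoga effect explained may be right or may be as low as about half, depending on how the mediator acts

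*Combined protocol and SAP*

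**What the plan says.** Section 9.6.1 (Objective 4, planned analyses) takes three steps.

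1. Each mediator is analysed as an outcome: "Intervention effects will first be estimated using LMMs, using the same modeling strategy used for objectives 1-3".
2. Changes in the mediators are correlated with change in incontinence frequency from baseline to 12 weeks.
3. The mediators are added to the primary model: "We will then examine attenuation of intervention effects estimates from the primary intention-to-treat analyses after adjustment for these potential mediators".

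If there is evidence of mediation, the proportion explained gets a bootstrap interval built from the treatment effects "before and after adjustment for change in the mediators". Mediators are continuous to begin with, and change in RSA and PEP is the example given.

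The model receiving the mediator is the Objective 1 model. It is fitted "adjusting for baseline incontinence frequency", and its other terms are given as: "In addition to fixed effects for study location and type of incontinence, the LMM will include terms for intervention, time, and the time-by-intervention interaction". No mediator baseline appears in it. Section 9.6.2 mentions baseline pelvic floor strength and physical function only as possible subgroup factors.

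The baseline values are part of the schedule. For the autonomic measures, section 6.1.6 says "participants will undergo the following measures at baseline and 12 weeks". Section 6.1.7 describes an "optional assessment of pelvic floor muscle strength at baseline and 12 weeks". Section 6.1.5 schedules physical performance at baseline, 6 and 12 weeks.

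**The concern.** Entering only the difference between the 12-week and baseline mediator forces the two values to carry equal and opposite coefficients. If leakage at 12 weeks depends on muscle strength or autonomic function at that time, the baseline part of the difference acts as noise. The mediator slope is then diluted, and part of the indirect effect is reported as direct.

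The plan is also uneven. Where the mediator is the outcome (step 1), the Objective 1 strategy implies adjustment for its baseline. Where the mediator is the explanatory variable (step 3), it does not.

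At stake is the reading of Hypothesis 4B. A real mediator could look weaker than it is. Because the interval is computed only if evidence of mediation is seen, a diluted slope could also end the analysis before any interval is reported.

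**Working it through.** **Starting point.** The plan gives no figure for the mediation step, so there is none to reproduce. It also gives no mediator SD, mediator correlation or path coefficient. Every such value below is an assumption. The check uses a single 12-week regression, without the class-series random effects or the 6-week visit.

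**Algebra.** Let T be arm, M0 and M12 the mediator at baseline and 12 weeks, D = M12 − M0, and Y0 baseline leakage. Write

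Y12 = c′T + b·M12 + d·M0 + g·Y0 + error.

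Substituting M12 = D + M0 turns the mediator terms into b·D + (b + d)·M0. If M0 is omitted, the within-arm slope on D becomes

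b + (b + d) × Cov(M0, D) / Var(D).

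Take equal mediator variances (set to 1), mediator correlation ρ, and M0 unrelated to Y0. Then Cov(M0, D) = −(1 − ρ), Var(D) = 2(1 − ρ), and their ratio is −1/2 whatever ρ is. The slope is b − (b + d)/2 = (b − d)/2. By randomisation the yoga effect on D equals its effect on M12, so the share explained scales with this slope.

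- Only change acts (d = −b): slope b, ratio of estimated to true share 1.00.
- Halfway (d = −b/2): slope 0.75b, ratio 0.75.
- Only the 12-week level acts (d = 0): slope b/2, ratio 0.50.

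**Unequal SDs, d = 0.** With 12-week SD equal to s times the baseline SD, the ratio is 1 + (ρs − 1)/(s² + 1 − 2ρs). For s = 0.9 and ρ = 0.5 this is 1 − 0.55/0.91 = 0.40; over ρ = 0.3 to 0.7 it runs from 0.43 down to 0.33. For s = 1.2 and ρ = 0.5 it is 1 − 0.40/1.24 = 0.68, with a range of 0.63 to 0.79.

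**Simulation, true share 0.50.** Yoga moves the mediator by 0.5 SD, b = −0.3 and the direct effect is −0.15. The indirect effect is 0.5 × (−0.3) = −0.15, and the share is 0.15/0.30 = 0.50. Mediator correlation is 0.4 to 0.8 with equal SDs.

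| How the mediator acts | Change only | With baseline mediator |
|---|---|---|
| 12-week level; baselines unrelated | 0.25 | 0.50 |
| 12-week level; baseline mediator–leakage correlation −0.3 | 0.26–0.27 | 0.50 |
| Halfway; baseline correlation −0.3 | 0.38 | 0.50 |
| Concurrent at each visit, plus stable person effect unrelated to mediator | 0.38–0.40 | 0.50 |
| As above, person effects correlated −0.3 | 0.39–0.40 | 0.57 |
| As above, person effects correlated −0.5 | 0.40 | 0.62–0.64 |
| Change only | 0.50 | 0.50 |

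Other parameter choices for the concurrent case with a shared stable factor gave 0.34 to 0.42 with change only, which is 16 to 32% low. With mediator reliability 0.7, both versions fall short: 0.11–0.23 for change only and 0.16–0.40 with baseline.

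**At trial size.** Completers are 240 × 0.85 = 204. In the 12-week-level case, the 5th to 95th percentile range of the estimated share was 0.07 to 0.83 for change only (median 0.26) and 0.21 to 1.20 with baseline (median 0.50). The chance that the mediator slope reached p < 0.05 fell from 99% with baseline to 68% without at mediator correlation 0.6, and from 88% to 39% at 0.8. These percentages depend on the assumed residual variance.

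**The case against.** **The plan matches its hypothesis.** Hypothesis 4B speaks of changes in incontinence mediated by changes in the factors. Under a pure change-to-change effect, the change-only model is unbiased. This stands. A reader might infer that the plan will halve the share explained, but the documents do not support that: halving needs only the 12-week level to act, and nothing in them says so. Wording a hypothesis in terms of change does not, however, force the baseline and 12-week coefficients to be equal and opposite. The model with baseline added contains the planned one as a special case.

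**The fix is not always right.** A reader might infer that adding the baseline always recovers the true share. It does not. When a stable unmeasured factor drives both mediator and leakage, the adjusted estimate overshoots. At a person-effect correlation of −0.5 it misses by 0.12 to 0.14, against 0.10 for change only. Mediator measurement error biases both versions downwards.

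**Precision is poor and the status exploratory.** Both points stand. Neither version gives a sharp share with about 204 women. Objective 4 is exploratory, mediator coding is left open, and no primary or secondary efficacy estimate changes. Nor does Hypothesis 4B rest on attenuation alone, since the correlation of changes comes first. That correlation describes the question asked, and replacing it would be a matter of preference.

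**Not every woman has a baseline value.** The pelvic floor examination is optional, and the autonomic measures may be declined during the pandemic. The physical performance battery named in 9.6.1 is not among the tests listed in 6.1.5. This affects how the models are fitted, not whether the covariate should be used.

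**Conclusion.** The concern holds with conditions. The plan adjusts for mediator change alone, and the model it builds on has no mediator baseline. With equal mediator SDs, the estimated share explained is unbiased if only change acts, about 20 to 30% too low if the mediator acts concurrently alongside a stable person effect, and about half the true value if only the 12-week level acts. It can be lower still if the mediator SD shrinks by 12 weeks. Which case applies cannot be read from the documents. The issue is confined to the interpretation of an exploratory objective. It gives no ground for doubting the primary intention-to-treat result.

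**What to change.** In section 9.6.1, Objective 4, state that each mediator's baseline value enters both the unadjusted and the mediator-adjusted models. Fit the two on the same women, namely those with baseline and 12-week values of that mediator. Otherwise the attenuation mixes mediation with a change of sample.

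Report the change-only version as a sensitivity analysis, and keep the correlation of changes as a descriptive result. State as a limitation that the baseline-adjusted share can overstate mediation if an unmeasured stable factor drives both mediator and leakage, and that mediator measurement error can bias it. Confirm that each physical function measure used as a mediator is collected at baseline.

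The cost is a sentence or two and one degree of freedom per mediator. The autonomic, pelvic floor and 2-minute step test baselines are already scheduled.

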2.2 Study Rationale

Yoga is a set of complementary physical and mental practices with the potential to improve urinary incontinence through multiple mechanisms, while also avoiding many of the shortcomings of existing clinical therapies. When taught in a way that emphasizes mindful awareness of specific bodily structures, yoga can be used to help women control and strengthen their pelvic floor muscles through a combination of group instruction and home practice. As a result, a group-based yoga program that incorporates practice of specific yoga postures to promote awareness and engagement of the pelvic floor may provide a more accessible alternative to traditional, one-on-one pelvic floor rehabilitation therapy.

Yogic breathing and relaxation techniques also have the potential to improve peripheral autonomic dysfunction as another potential contributor to incontinence. Prior physiologic studies have demonstrated that many women with urgency-type incontinence have to have abnormalities in sympathetic and parasympathetic autonomic function.²⁰⁻²⁵ Yoga interventions that involve regular practice of yogic breathing have the potential to improve resting autonomic function as well as stress-related autonomic reactivity,²⁶⁻²⁹ which could in turn lead to improved bladder control.

Regular practice of yoga postures can also improve physical deconditioning as another

potential contributor to incontinence risk.^{5,30-33} Among frail older women, decreased physical conditioning and mobility can compromise women's ability to get to the bathroom when they experience urges to urinate. Poor physical conditioning is also associated with increased abdominal obesity, which has been shown to contribute to both stress- and urgency-type incontinence symptoms. Several small studies have explored the benefits of physical exercise programs for preventing or managing incontinence in older women^{34,35}; unlike yoga, however, these non-specific exercise programs did not have the added benefit of engaging the pelvic floor or directly improving autonomic balance in incontinent women.

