Planned analyses: Additional LMMs will examine other secondary outcomes including incontinence-related quality of life as assessed by validated questionnaires (i.e., the Incontinence Impact Questionnaire (IIQ), Urogenital Distress Inventory (UDI), Patient Perception of Bladder Condition (PPBC), Pelvic Organ Prolapse/Incontinence Sexual Questionnaire, and IUGA-Revised (PISQ-IR) questionnaire), as well as depression and anxiety symptoms assessed by additional questionnaires (i.e., the Center for Epidemiology Studies Depression Scale (CES-D), Hospital and Anxiety Depression Scale (HADS), and State Trait Anxiety Inventory (STAI)). We will again estimate intention-to-treat intervention effects, adjusting for study location, using the same modeling strategy as for objective 1. Transformation or categorization of questionnaire scores (in combination with logistic or proportional odds models) will be considered as needed to deal with skewness of outcomes.

Objective 4: To explore whether the yoga intervention is associated with improvements in 1) pelvic floor muscle strength, 2) peripheral autonomic function, and/or 3) lower extremity physical function, and assess whether improvements in these factors may mediate improvement in incontinence.

Hypothesis 4A: Among ambulatory incontinent women enrolled in this trial, the yoga intervention will be associated with improvements in a) pelvic floor muscle strength (assessed by pelvic exam), b) cardiac autonomic function (assessed by heart rate variability and impedance cardiography), and c) lower extremity physical function (assessed by physical performance assessment) over 12 weeks.

Hypothesis 4B: Among ambulatory incontinent women enrolled in this trial, changes in incontinence frequency over 12 weeks will be partly mediated by changes in a) pelvic floor muscle strength, b) cardiac autonomic function, and c) lower extremity physical function.

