Exploratory subgroup analyses. Intervention effects will be analyzed in subgroups in multivariate analysis based on a limited set of clinicopathologic factors that are hypothesized to have the potential to influence participants' response to the yoga and stretching/strengthening interventions. For example, we may explore whether baseline participant age, race/ethnicity, clinical type of incontinence, pelvic floor muscle strength, or physical function levels influence subsequent treatment-associated changes in primary and secondary outcomes. Subgroup-specific effects, estimated using the interaction model, will be presented only if the interaction between treatment and subgroup is statistically significant at $p < 0.05$.

During the COVID-19 pandemic, intervention instruction in some study waves may be converted to remote platforms (i.e., interactive video-based class instruction rather than in-person class instruction). In that event, we will use the methods outlined above for exploratory subgroup analyses to evaluate differences in the effect of the intervention in waves that rely primarily on video-based instruction rather than in-person instruction.

Co-intervention effects. Because awareness of intervention assignment can affect use of co-interventions, women in both groups will be asked to refrain from using other clinical incontinence treatments during the study. Nevertheless, information about co-interventions will be collected at follow-up visits to permit assessment of potential effects of differential use of co-interventions on outcomes. To estimate the direct effect of the intervention in the absence of co-interventions, we may conduct additional analyses to add co-intervention use, as well as confounders of its effect on the outcome, to the primary treatment model; if factors that are also affected by the co-interventions are among the confounders, we may use inverse weighting rather than direct adjustment for this purpose.

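### The exploratory mediation analysis adds only the mediators to the primary model, so uncontrolled common causes of mediator and incontinence change can inflate or hide the share of the yoga effect reported as explained

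*Combined protocol and SAP*

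**What the plan says.** Section 9.6.1 introduces Objective 4 in exploratory terms: "To explore whether the yoga intervention is associated with improvements in 1) pelvic floor muscle strength", and likewise for autonomic and lower extremity function. Hypothesis 4B is that change in these factors partly mediates change in incontinence frequency over 12 weeks.

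The analysis has four steps. Intervention effects on the mediators are estimated first. Changes in the mediators are then correlated with change in incontinence. Next, "We will then examine attenuation of intervention effects estimates from the primary intention-to-treat analyses after adjustment for these potential mediators". Finally, if there is evidence of mediation (not defined), the plan reports "95% bias-corrected percentile confidence intervals for the proportion of intervention effect explained".

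The primary model is also set out in 9.6.1. It works by "adjusting for baseline incontinence frequency", and: "In addition to fixed effects for study location and type of incontinence, the LMM will include terms for intervention, time, and the time-by-intervention interaction". It has random effects for class series and participant. The mediation step names no further covariate. It does not state an assumption of no unmeasured confounding, and it plans no sensitivity analysis for that assumption.

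Two other places bear on the point. Section 6.1.8 lists other baseline data but ties their use in adjustment to imbalance between the arms. Section 9.6.2, on co-interventions, does provide for confounders: "we may conduct additional analyses to add co-intervention use, as well as confounders of its effect on the outcome, to the primary treatment model", with inverse weighting as an alternative.

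**The concern.** A change in pelvic floor strength, autonomic function or fitness is observed after randomization, not assigned. Within an arm, women whose mediator improves may differ from the others in age, weight, general health or activity, and those differences may also affect how much their incontinence improves. The mediator's coefficient in the outcome model then contains shared prognosis as well as any causal effect. The drop in the yoga estimate when the mediator is added inherits that mixture.

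The adjustment trigger in 6.1.8 does not help, because perfectly balanced arms would leave this bias in place. Resampling participants does not help either: it puts an interval around the biased quantity.

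At stake is the answer to Hypothesis 4B. A factor that does nothing could be reported as a partial mechanism of yoga, or a real mechanism could be understated.

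**Working it through.** **Anchor for the total effect.** The documents give no figure for the mediation analysis, so the only plan figure to reproduce is the sample size in 9.2.
- Inputs: baseline 23 to 24 episodes/week, SD of change 14.4, correlation 0.59, a 20% difference, 15% loss, 80% power, two-sided 5%.
- Residual SD = 14.4 × √(1 − 0.59²) = 11.63. A difference of 20% × 23 = 4.6 needs 101 per arm. Then 101/0.85 gives 119 per arm, 238 in total, against the plan's 240. With 102 per arm analysed, power is 80.7%.
- This works only at the low end of the baseline range, with 14.4 treated as the SD before the correlation adjustment. The point here does not depend on it.

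**Inputs for the bias.**
- Total effect τ: 20% × 23.5 = 4.7 episodes/week, and 4.7/14.4 = 0.33 SD.
- Yoga effect on a mediator, a: not given. Assumed 0.26 to 0.39 SD, borrowed from the differences that 9.2 calls detectable for secondary outcomes.
- Correlation r of an omitted common cause with each of the two changes, within arm: not given. Assumed 0.1, 0.3 and 0.5.
- Effect of the mediator on incontinence: set to zero.

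**Formula.** Let T be the arm, U the common cause, M the mediator change and Y the improvement in incontinence, with total within-arm SDs of 1:

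M = aT + rU + √(1 − r²)·e₁ and Y = τT + rU + √(1 − r²)·e₂.

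With U omitted, the coefficient of M given T is cov(M, Y | T)/var(M | T) = r². The yoga estimate falls from τ to τ − a·r², so the share labelled as explained is a·r²/τ. The total SDs must be 1. If the error terms alone had SD 1, the coefficient would be r²/(1 + r²).

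**Results when the true mediated share is 0.**

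| a | r = 0.1 | r = 0.3 | r = 0.5 |
|---|---|---|---|
| 0.26 | 0.8% | 7.2% | 19.9% |
| 0.39 | 1.2% | 10.8% | 29.9% |

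For example, 0.39 × 0.3²/0.3264 = 0.0351/0.3264 = 10.8%. Dividing by 11.63 instead of 14.4 multiplies every share by 11.63/14.4 = 0.81, giving about 6% to 9% at r = 0.3 and 16% to 24% at r = 0.5.

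**Simulation check.** Ordinary least squares, one mediator with no effect, 204 women (2 × 102), 4,000 runs per cell.
- Mean shares agree with the formula: 0.9%, 7.1% and 19.8% for a = 0.26; 1.4%, 11.0% and 30.2% for a = 0.39.
- Both paths (yoga to mediator, mediator to outcome) are significant in 2%, 11% and 44% of runs for a = 0.26, and in 4%, 20% and 74% for a = 0.39.
- With U in both models, the share is within 0.2 percentage points of zero and both paths are significant in 2% to 4% of runs. This assumes that U is fully measured.
- If U acts in opposite directions (r = 0.3 and −0.3, a = 0.39), the share is −10.9%.
- If yoga does not move the mediator (a = 0, r = 0.5), the mean share is −0.2%, in effect zero.

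The simulation leaves out class clustering and the repeated-measures model. Significance of both paths stands in for the plan's undefined evidence of mediation.

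**The case against.** The strongest reply is that the aim is exploratory, no efficacy conclusion depends on it, and the proportion explained gets an interval only if mediation appears. The primary model is also not bare: confounding that runs through baseline incontinence, location or incontinence type is already removed. All of this stands and limits the weight of the point. It does not make the estimate interpretable, because Hypothesis 4B is a causal statement with a planned numerical answer.

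The size rests on assumed inputs. The 0.26 to 0.39 SD range is not a forecast for mediators. A value of r = 0.5 means that one cause, beyond the existing covariates, explains 25% of the within-arm variance in both changes, and nothing in the documents supports that. This also stands.

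Several stronger readings are tempting and are not supported:
- A reader might infer that section 2.2 establishes the common cause: "Poor physical conditioning is also associated with increased abdominal obesity, which has been shown to contribute to both stress- and urgency-type incontinence symptoms". That sentence describes a possible pathway through conditioning, or an association of levels. It does not show that body weight drives both 12-week changes.
- A reader might infer that the bias always creates false mediation. Its direction is unknown.
- A reader might infer that 9.6.1 breaks a standard set by 9.6.2. The co-intervention analysis, to "add co-intervention use, as well as confounders of its effect on the outcome, to the primary treatment model", is optional. It shows that the plan recognizes the problem, not that it requires this handling everywhere.

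**Conclusion.** The point holds as a limitation of the exploratory mediation analysis. As written, attenuation is measured without control of mediator-outcome confounders beyond baseline incontinence frequency, location and incontinence type. The proportion explained can therefore be too high or too low, by an amount its interval does not reflect.

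Under the stated assumptions the error ranges from negligible with a weak common cause, through roughly a tenth of the effect at r = 0.3, to as much as 30% at r = 0.5. It needs both a yoga effect on the mediator and a residual common cause.

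The documents do not show that such a cause exists at any particular strength. It would be wrong to conclude that a mediation finding from this trial must be spurious, or that the primary comparison is compromised.

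**What to change.** In 9.6.1, Objective 4:
- Fix in advance a short set of baseline covariates already collected: the baseline value of each mediator (6.1.5 to 6.1.7) and, from 6.1.8, age, body mass index, general health or diabetes, activity level and menopausal status. Put the same set in the model without the mediator and in the model with it.
- Add one sensitivity analysis showing how strong a residual common cause would have to be to remove the estimated mediation.
- State that baseline adjustment does not remove common causes arising after randomization, such as home practice (5.4) and self-directed pelvic muscle exercises prompted by the pamphlet (5.3.1), and that the estimate is exploratory for that reason. Alternatively, handle them by weighting, as 9.6.2 allows for co-interventions.

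The cost is SAP wording, a few degrees of freedom, and simple imputation for women missing a baseline covariate. No new data collection is needed. Baseline adjustment reduces the bias but does not guarantee that the difference between the two models reflects the mediator alone, which is why the sensitivity analysis is needed.
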